5.8.2. Analysis of Adverse Events of Special Interest

- Treatment-emergent adverse events of special interest (AESI), as listed in Section 4.8.1.2, will be presented by SOC and PT as applicable. AESI are defined by SMQ, CMQ, and/or dedicated e-CRF as described in Appendix 10.3 .

The following variables will also be tabulated for infusion reactions TEAEs:

- Intensity of the event (mild, moderate, severe or very severe);
- Number of events divided by the number of study treatment administrations received in treatment period;
- Time from first study treatment to first infusion reaction;

5.8.3. Clinical Laboratory Measurements

Clinical laboratory parameter actual values (quantitative) and change from baseline values will be descriptively summarized at baseline and each post-baseline visit for the open-label treatment (OLTP) period, by at least patient number, mean, median, Q1, Q3, SD, minimum and maximum.

Clinical laboratory parameters mean changes from baseline, with the corresponding SE, can be plotted at each visit in the case results warrant further investigation. These parameters will be presented by the biological functions defined in Section 4.8.2. For glucose, only fasting samples will be included in the summaries.

Individual patient laboratory parameter measurements will be additionally evaluated by PCSV criteria (See Appendix 10.4), specifically identifying patients with at least one post-baseline measurement that meets the PCSV criteria within the TEAE period. These laboratory parameters will be presented by the biological functions defined in Section 4.8.2. The incidence of PCSVs at any time during the TEAE period will be summarized regardless of the baseline level, and again according to the following baseline categories:

- Normal (according to PCSV criterion/criteria)/missing
- Abnormal according to PCSV criterion or criteria

Patient listings of laboratory measurements that meet PCSV criteria will be provided for the report appendix.

For those laboratory parameters that don't have an associated PCSV criteria, similar summary tables can be provided based on measurements outside the central laboratory normal ranges, if applicable.

Drug-induced liver injury

For the treatment period, an evaluation of drug-induced serious hepatotoxicity (eDISH) with the graph of distribution of peak values of ALT versus peak values of total bilirubin will also be presented using post-baseline values during TEAE period. Note that the ALT and total bilirubin values are presented on a logarithmic scale. The graph will be divided into 4 quadrants with a vertical line corresponding to 3 x ULN for ALT and a horizontal line corresponding to 2 x ULN for total bilirubin.

Patient listing of possible Hy's law cases identified by patient group (i.e., patients with any elevated ALT > 3 x ULN, and associated with an increase in bilirubin > 2 x ULN, concomitantly or not) with ALT, AST, ALP, total bilirubin, and if available direct and indirect bilirubin will be provided.

The summary of clinical laboratory parameter measurements will be provided for all patients in the study in the safety analysis set, and again for the subpopulation of adolescent patients.

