- Alanine aminotransferase (ALT) or aspartate aminotransferase (AST) >3 x upper limit of normal (ULN) (1 repeat lab is allowed)
- CPK >3 x ULN (1 repeat lab is allowed)
- Positive serum beta-human chorionic gonadotropin or urine pregnancy test in WOCBP

- TSH >1.5 x ULN of the central laboratory (1 repeat lab is allowed) for patients not on thyroid replacement therapy
- Positive test for hepatitis B surface antigen and/or hepatitis C antibody (associated with a positive HCV RNA polymerase chain reaction)
- eGFR <30 mL/min/1.73 m² (calculated by central lab)
- Postmenopausal status will be confirmed by measurement of follicle-stimulating hormone (FSH)

12. Member of the clinical site study team and/or his/her immediate family.

13. Pregnant or breastfeeding women.

14. Women of childbearing potential* who are unwilling to practice highly effective contraception prior to the initial dose/start of the first treatment, during the study, and for at least 24 weeks after the last dose of study drug. Highly effective contraceptive measures include:

- a. stable use of combined (estrogen and progestogen containing) hormonal contraception (oral, intravaginal, transdermal) or progestogen-only hormonal contraception (oral, injectable, implantable) associated with inhibition of ovulation initiated 2 or more menstrual cycles prior to screening
- b. intrauterine device (IUD); intrauterine hormone-releasing system (IUS)
- c. bilateral tubal ligation
- d. vasectomized partner
- e. and/or sexual abstinence†, ‡

*Postmenopausal women must be amenorrheic for at least 12 months in order **not** to be considered of childbearing potential. Pregnancy testing and contraception are not required for women with documented hysterectomy, and/or oophorectomy.

Oocyte donation is prohibited during the study and for 24 weeks after the last administration of study drug.

† Sexual abstinence is considered a highly effective method only if defined as refraining from heterosexual intercourse during the entire period of risk associated with the study treatments. True abstinence: when this is in line with the preferred and usual lifestyle of the patient.

‡ Periodic abstinence (calendar, symptothermal, post-ovulation methods), withdrawal (coitus interruptus), spermicides only, and lactational amenorrhoea method (LAM) are not acceptable methods of contraception. Female condom and male condom should not be used together.

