9.4.3. Other Events that Require Accelerated Reporting to Sponsor

The following events also require reporting to the sponsor (or designee) within 24 hours of learning of the event:

Symptomatic Overdose of Study Drug: Accidental or intentional overdose of at least 2 times the intended dose of study drug within the intended therapeutic window, if associated with an AE,

Pregnancy: Although pregnancy is not considered an AE, it is the responsibility of the investigator to report to the sponsor (or designee), within 24 hours of identification, any pregnancy occurring in a female patient or female partner of a male patient, during the study or within 24 weeks of the last dose of study drug. Any complication of pregnancy affecting a female study patient or female partner of a male study patient, and/or fetus and/or newborn that meets the SAE criteria must be reported as an SAE. Outcome for all pregnancies should be reported to the sponsor.

Adverse Events of Special Interest: All AESI, serious and nonserious, must be reported within 24 hours of identification using the same reporting process as for SAE reporting, per Section 9.4.2.

Adverse events of special interest for evinacumab include the following:

- Anaphylactic reactions
- Moderate or severe infusion reactions

- Increase in ALT or AST: ≥ 3 x ULN (if baseline <ULN), or ≥ 2 times the baseline value (if baseline \geq ULN)
- Allergic events and/or local injection site reactions that require medical treatment or that require consultation with another physician for further evaluation
- Pregnancy
- Symptomatic overdose with investigational medicinal product
- Neurocognitive events
- New onset of diabetes*
- Pancreatitis

Adverse events of special interest for alirocumab include the following:

- Increase in ALT: ALT ≥ 3 x ULN (if baseline ALT <ULN), or ALT ≥ 2 times the baseline value (if baseline ALT \geq ULN)
- Allergic events and/or local injection site reactions that require consultation with another physician for further evaluation
- Pregnancy
- Symptomatic overdose with investigational medicinal product
- Neurologic events that require additional examinations/procedures and/or referral to a specialist
- Neurocognitive events
- Cataracts
- New onset of diabetes*

*New onset of diabetes is defined as any of the following:

- Type 1 or type 2 diabetes TEAE (grouping of MedDRA terms will be specified in the statistical analysis plan [SAP])

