10.4. Criteria for Potentially Clinically Significant Values (PCSV)

Parameter	PCSV
Clinical chemistry	
ALT	By distribution analysis: >2 ULN and baseline ≤ 2 ULN >3 ULN and baseline ≤ 3 ULN >5 ULN and baseline ≤ 5 ULN >10 ULN and baseline ≤ 10 ULN >20 ULN and baseline ≤ 20 ULN
AST	By distribution analysis: >2 ULN and baseline ≤ 2 ULN >3 ULN and baseline ≤ 3 ULN >5 ULN and baseline ≤ 5 ULN >10 ULN and baseline ≤ 10 ULN >20 ULN and baseline ≤ 20 ULN
Alkaline Phosphatase	> 1.5 ULN and baseline ≤ 1.5 ULN
Total Bilirubin	> 1.5 ULN and baseline ≤ 1.5 ULN > 2 ULN and baseline ≤ 2 ULN
Conjugated bilirubin	> 35% total bilirubin (when total bilirubin >1.5 ULN)
ALT and Total Bilirubin	ALT > 3 ULN and Total Bilirubin > 2 ULN and baseline ALT ≤ 3 ULN or Total bilirubin ≤ 2 ULN
CPK	> 3 ULN and ≤ 5 ULN and baseline ≤ 3ULN >5 ULN and ≤ 10 ULN and baseline ≤ 5 ULN >10 ULN and baseline ≤ 10 ULN
Creatinine	≥ 150 μmol/L (adults) ≥ 30% from baseline ≥ 100% from baseline
CLcr (mL/min) (Estimated creatinine clearance based on the Cockcroft-Gault equation)	≥15 - <30 (severe decrease in GFR) ≥30 - < 60 (moderate decrease in GFR) ≥60 - <90 (mild decrease in GFR) ≥ 90 (normal GFR)
eGFR (mL/min/1.73m2) (Estimate of GFR based on an MDRD equation)	≥15 - <30 (severe decrease in GFR) ≥30 - < 60 (moderate decrease in GFR) ≥60 - <90 (mild decrease in GFR) ≥ 90 (normal GFR)

Parameter	PCSV
Uric Acid Hyperuricemia: Hypouricemia:	>408 µmol/L <120 µmol/L
Blood Urea Nitrogen	≥17 mmol/L
Chloride	<80 mmol/L >115 mmol/L
Sodium	≤129 mmol/L ≥ 160 mmol/L
Potassium	< 3 mmol/L ≥ 5.5 mmol/L
Glucose Hypoglycaemia Hyperglycaemia	≤ 3.9 mmol/L and < LLN ≥ 7 mmol/L (fasted); ≥ 11.1 mmol/L (unfasted)
HbA1c	>8%
Albumin	≤25 g/L
Hs-CRP	> 2 ULN or >10 mg/L, if ULN not provided
Hematology	
WBC	< 3.0 Giga/L (3000/ mm ³) (Non-Black) < 2.0 Giga/L (2000/ mm ³) (Black) ≥16.0 Giga/L (16000/ mm ³)
Lymphocytes	>4.0 Giga/L
Neutrophils	< 1.5 Giga/L (1500/ mm ³) (Non-Black) < 1.0 Giga/L (1000/ mm ³) (Black)
Monocytes	>0.7 Giga/L
Eosinophils	> 0.5 Giga/L (500/ mm ³) or > ULN if ULN ≥ 0.5 Giga/L
Hemoglobin	≤115 g/L (Male); ≤95 g/L (Female) ≥185 g/L (Male); ≥165 g/L (Female) Decrease from Baseline ≥15 g/L Decrease from Baseline ≥20 g/L
Hematocrit	≤0.37 v/v (Male) ; ≤0.32 v/v (Female) ≥0.55 v/v (Male) ; ≥0.5 v/v (Female)
RBC	≥6 Tera/L

Parameter	PCSV
Platelets	< 100 Giga/L (100 000/mm ³) ≥700 Giga/L (700000/mm ³)
Urinalysis	
pH	≤4.6 ≥8
Vital signs	

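### The SAP's joint liver-injury displays are triggered by ALT only, so a patient with AST above 3 x ULN and bilirubin above 2 x ULN, but ALT never above 3 x ULN, is not flagged as a possible Hy's law case

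*SAP*

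**What the plan says.** SAP 5.8.3, under drug-induced liver injury, plans two displays. The first is an eDISH "graph of distribution of peak values of ALT versus peak values of total bilirubin", using post-baseline values in the TEAE period and divided into quadrants by a "vertical line corresponding to 3 x ULN for ALT and a horizontal line corresponding to 2 x ULN for total bilirubin". The second is a patient listing of possible Hy's law cases, defined as "patients with any elevated ALT > 3 x ULN, and associated with an increase in bilirubin > 2 x ULN", whether or not the two rises coincide in time. AST is a column of that listing, which is to be presented "with ALT, AST, ALP, total bilirubin, and if available direct and indirect bilirubin will be provided", but it plays no part in selecting patients.

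SAP 10.4 has separate PCSV rows for ALT, AST and total bilirubin. Its one row that joins an aminotransferase to bilirubin reads "ALT > 3 ULN and Total Bilirubin > 2 ULN", followed by a baseline condition, "baseline ALT ≤ 3 ULN or Total bilirubin ≤ 2 ULN". There is no matching row for AST with bilirubin.

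Protocol 9.4.3 defines the hepatic adverse event of special interest for evinacumab as an "Increase in ALT or AST". The threshold is at least 3 x ULN when baseline is below ULN, and at least twice baseline otherwise. Protocol 6.2.2, criterion 11, excludes evinacumab-naïve patients at screening on "Alanine aminotransferase (ALT) or aspartate aminotransferase (AST) >3 x upper limit of normal (ULN").

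**The concern.** Safety is the primary endpoint (Protocol 4.2, SAP 4.7.1), and the study has a single arm and no formal testing, so serious liver injury will be judged patient by patient. The Hy's law listing, the eDISH quadrant and the combined PCSV row are the outputs that put an aminotransferase rise and a bilirubin rise together in one patient. All three ask only about ALT.

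For the study drug, the protocol treats a rise in either enzyme as the reportable hepatic event. A patient can therefore meet that event through AST, also have bilirubin above 2 x ULN, and still not be labelled a possible Hy's law case. SAP 10.3 (Table 2) gives hepatic disorders no tick box on the case report form. It identifies them by a MedDRA query, the PCSVs and the Hy's law eDISH plot, so these displays form part of how the event is found. What is at stake is a report statement that no possible Hy's law case occurred when a patient's own data, viewed jointly, would call for review.

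**Working it through.** The plan states no figure to reproduce, and no power or sample-size quantity is involved. The check applies the written rules to example patients.

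**Rules, in multiples of ULN**

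- Hy's law listing and eDISH Hy's law quadrant (SAP 5.8.3): peak ALT > 3 and peak total bilirubin > 2.
- Combined PCSV (SAP 10.4): ALT > 3 and total bilirubin > 2, with the baseline condition read as one clause.
- AST PCSV (SAP 10.4): AST > 3 with baseline ≤ 3.
- Bilirubin PCSV (SAP 10.4): total bilirubin > 2 with baseline ≤ 2.
- Protocol 9.4.3 event for evinacumab, for baseline below ULN: ALT ≥ 3 or AST ≥ 3.
- Proposed rule: (ALT > 3 or AST > 3) and total bilirubin > 2.

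**Assumed patients.** The values are illustrative. Every baseline is set to 0.8 x ULN, so all baseline conditions are met.

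| ALT | AST | Bilirubin | Three joint outputs | AST PCSV | Bilirubin PCSV | Protocol event | Proposed rule |
|---|---|---|---|---|---|---|---|
| 2 | 4 | 2.5 | no | yes | yes | yes | yes |
| 2.9 | 6 | 3 | no | yes | yes | yes | yes |
| 4 | 4 | 2.5 | yes | yes | yes | yes | yes |
| 4 | 2 | 2.5 | yes | no | yes | yes | yes |

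The first two patients meet the protocol's hepatic event and both single-parameter PCSVs, yet none of the three joint outputs flags them. In the first, AST 4 > 3 and bilirubin 2.5 > 2, but ALT 2 is not above 3. The last two are flagged because ALT 4 > 3, and the proposed rule leaves their classification unchanged.

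The gap therefore needs three things at once: AST > 3, bilirubin > 2, and ALT at or below 3 throughout the TEAE period. Because the listing pairs values whether or not they coincide, a single ALT value above 3 at any point in that period closes the gap.

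**Where the first two patients do appear.** SAP 5.8.3 provides patient listings of values meeting PCSV criteria, so their AST and bilirubin values are both listed. On eDISH they lie above the bilirubin line and to the left of the ALT line. They are visible, but outside the Hy's law quadrant. Nothing in SAP 5.8.3, 10.3 or 10.4 directs anyone to match the AST and bilirubin listings.

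**The case against.** The strongest reply is that such a patient is hardly hidden. Both abnormal values are listed at patient level, the patient is plotted on eDISH, and the hepatic event in SAP 10.3 also draws on all the PCSVs and a MedDRA query. Outside the analysis, Protocol 9.4.3 requires the AST rise to be reported within 24 hours, Protocol 8.2.2.5 requires significantly abnormal results to be repeated, and the sponsor and the IDMC review accumulating safety data. In a study of about 120 patients, a real case would probably be noticed. All of this stands. A reader might infer that the patient drops out of the report altogether, and the documents do not support that. What remains is narrower: no output joins the two findings, and the listing meant to do so returns nothing for this patient.

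A reader might also infer that the SAP contradicts the protocol. It does not. The protocol has no Hy's law definition, eDISH specification or combined liver criterion. Section 9.4.3 is a reporting trigger and section 6.2.2 an eligibility rule, and the 9.4.3 event for background alirocumab is ALT-only. The mismatch is between the study drug's reporting trigger and the chosen displays, and it is a reason to improve the displays.

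Finally, AST can rise from muscle, and statins are permitted background therapy. That is a fair caution. However, the proposed rule also demands bilirubin above 2 x ULN, CPK is already in the chemistry panel (Protocol 8.2.2.5), and a listing of possible cases is a prompt for review, not a diagnosis.

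**Conclusion.** The point holds in this limited form. As written, a patient with AST above 3 x ULN, total bilirubin above 2 x ULN and peak ALT at or below 3 x ULN is not flagged as a possible Hy's law case by any joint display, and the report could state that there were none. This follows from the wording of SAP 5.8.3 and 10.4 and needs no assumption beyond such a patient occurring.

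Its size cannot be computed, because the documents give no rate of AST-only elevation with raised bilirubin. It is tempting to cite the upper bound for zero events in 120 patients, 3/120 = 2.5%. That bound applies to any event not observed, under any definition, and says nothing about how many AST-only cases to expect. The case for change is that the displays exist to find single cases, the data are already collected, and the correction is small. It is a worthwhile, inexpensive improvement to primary safety reporting, not a defect that invalidates it.

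**What to change.** 1. In SAP 5.8.3, define possible Hy's law cases as (ALT or AST) > 3 x ULN with total bilirubin > 2 x ULN, keeping the rule that the rises need not coincide.
2. In SAP 10.4, change the combined row to (ALT or AST) and Total Bilirubin, and extend its baseline clause to name AST.
3. On eDISH, plot the larger of ALT/ULN and AST/ULN for each patient, or add a second panel for AST.
4. Add CPK to the Hy's law listing so that AST rises of muscle origin can be recognised.

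No new data are needed, and patients with ALT above 3 x ULN are classified as before. The cost is a few lines of SAP text, a small program change, and an occasional line of review for an AST rise that turns out to be of muscle origin.

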5.8.4. Analysis of Vital Signs

The vital sign actual values and change from baseline values obtained while sitting will be descriptively summarized at baseline and each post-baseline visit for the open-label treatment (OLTP) period, by at least patient number, mean, median, Q1, Q3, SD, minimum and maximum. Vital signs mean changes from baseline, with the corresponding SE, can be plotted at each visit in the case results warrant further investigation.

Individual patient vital sign measurements (regardless of sitting position) will be additionally evaluated by PCSV criteria, specifically identifying patients with at least one post-baseline measurement that meets the PCSV criteria within the TEAE period. The incidence of PCSVs at any time during the TEAE period will be summarized regardless of the baseline level, and again according to the following baseline categories:

- Normal (according to PCSV criterion/criteria)/missing
- Abnormal according to PCSV criterion or criteria

Patient listings of vital sign measurements that meet PCSV criteria will be provided for the report appendix.

The summary of vital signs will be provided for all patients in the study in the safety analysis set, and again for the subpopulation of adolescent patients.

5.8.5. Analysis of 12-Lead ECG

For the treatment period, ECG parameters will be described through an overall interpretation of ECG status (e.g. normal, abnormal [clinically significant (Yes/No)]). The count and percentage of patients with at least 1 abnormal post-baseline ECG during the TEAE period will be summarized according to the following baseline status categories:

- Normal/missing;
- Abnormal

Individual patient ECG measurements will be additionally evaluated by PCSV criteria, specifically identifying patients with at least one post-baseline measurement that meets the PCSV criteria within the TEAE period. The incidence of PCSVs at any time during the respective TEAE periods will be summarized regardless of the baseline level, and again according to the following baseline categories:

- Normal (according to PCSV criterion/criteria)/missing
- Abnormal according to PCSV criterion or criteria

Patient listings of ECG measurements that meet PCSV criteria will be provided for the report appendix.

The summary of ECG data will be provided for all patients in the study in the safety analysis set, and again for the subpopulation of adolescent patients.

5.8.6. Physical Exams

A list of patients with any clinically significant abnormality results will be generated.

The summary of physical exams will be provided for all patients in the study in the safety analysis set, and again for the subpopulation of adolescent patients.

5.9. Analysis of Other Variables

Summaries for the treatment period will be presented by patient group for the study in the safety analysis set. No formal inferential testing will be performed. Summaries will be descriptive in nature.

All measurements, scheduled or unscheduled, fasting or not fasting, will be assigned to Global Analysis Windows (Appendix 10.2) in order to provide an assessment for all post-baseline visit.

Hs-CRP, HbA1c, HDL-C, Apo A1, and Apo B/Apo A1 ratio, Lp(a), Apo CIII parameters will be summarized for the number of patients with data, mean, SD, median, minimum, maximum, Q1 and Q3 by analysis visit during the treatment period. The medians (with Q1-Q3) will be plotted for hs-CRP, and means (+/- SE) for HbA1c, HDL-C, Apo A1, and Apo B/Apo A1 ratio, Lp(a), Apo CIII. Applying the PCSV criteria at any time during the TEAE period, the number of patients (and percentages) meeting the criteria will be summarized.

The summary of other variables will be provided for all patients in the study in the safety analysis set, and again for the subpopulation of adolescent patients.

5.10. Analysis of Pharmacokinetic Variables

Descriptive statistics of concentrations of total evinacumab, total ANGPTL3 will be presented. Mean concentrations of each analyte will be tabulated by visit for the study in the PK analysis set, with concentrations below the LLOQ set to zero.

Plots of the mean concentrations (linear and log scales) will be presented by nominal sampling time. Plots of the individual concentrations (linear and log scales) will be presented by actual sampling time. In the linear-scaled plots, concentrations below the LLOQ will be set to zero; in the log-scaled plots, concentrations below the LLOQ will be imputed as LLOQ/2.

Descriptive comparison of concentrations of evinacumab and total ANGPTL3 between Caucasian patients and Japanese patients may be performed if sufficient data are collected.

Concentrations of evinacumab measured before and post apheresis procedure will be summarized descriptively. Other descriptive sub-group analyses may be performed as appropriate, including concomitant medications, parent studies, previous treatment with evinacumab, adolescents, renal impairment, etc.

When appropriate, relationship between concentrations of evinacumab and LDL-C or other biomarkers may be evaluated descriptively.

The summary of pharmacokinetic variables will be provided for all patients in the study in the safety analysis set, and again for the subpopulation of adolescent patients.

5.11. Analysis of Immunogenicity Variables

The summary of immunogenicity variables will be provided for all patients in the study in the safety analysis set, and again for the subpopulation of adolescent patients.

